8.4 Reporting and Exclusions

All patients enrolled in this study who complete at least 60Gy of radiation and follow up at 30 days post treatment will be included in the analysis.

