2 OBJECTIVES

2.1 Safety/Efficacy

2.1.1 Primary Objective

A. Determine if objectively lower rates of significant radiation dermatitis occur with Dermaprazole for HNC patients receiving radiation when compared to patients receiving Aquaphor. An objective measure will be tabulated: the rate of clinically significant (CTCAE version 5 grade 2 or higher) radiation dermatitis. This measure will be reported weekly during treatment by both the treating radiation oncologist and blinded review by a board-certified dermatologist via medical photography.

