The effect of radiation on the skin is in part due to its effect in promoting the production of highly reactive free radicals that are involved in DNA damage. In addition, radiation upregulates inflammatory cytokines (M. A. Brach, 1993) (e.g., $TNF\alpha$, $IL1\beta$, IL6, VCAM1 and ICAM1) that can exacerbate sustained injury and compromise skin integrity. Almost all head and neck cancer patients are profoundly affected by severe dermatitis (Grade II or higher) due to the development of serious skin reactions described above. The predictive risk factors for prolonged effect of severe dermatitis include age, sex, body mass index (BMI), site and volume of the body exposed to radiation, use of concurrent radiosensitizing drugs or chemotherapy regimen and presence of diabetes, autoimmune disorders, or genetic mutations (F. Meyer). Severe dermatitis can result in discontinuation of the radiotherapy before completion of the prescribed dose and threatens the relapse of underlying cancer (S. A. McCloskey, 2009), (Asa Bostrom, 2001).

Page 5 of 23

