5.4 Intervention

Head and neck radiation treatment will follow standard practice. Variations (dose adjustments, delays, etc) that follow standard clinical practice are allowed and are not considered deviations, though these will be recorded to assess for interference.

Patients will be managed with twice daily prophylactic use of the proposed intervention (Dermaprazole) topical cream for radiation dermatitis or Aquaphor. The amount of cream or Aquaphor will be 2cc per application and will be measured in pre-filled capped syringes for every application.

The Dermaprazole topical cream will be manufactured by Village Pharmacy in Houston. After the product is compounded it will be overnight shipped to the Mays Cancer Center Pharmacy in insulated shipping containers with temperature monitors. The cream will be

Page 9 of 23

stable for a minimum of 60 days in airtight containers under refrigerated conditions ($2^{\circ} - 8^{\circ}$ C) and is stable at controlled room temperature for at least 1 week. Room temperature is 20° C – 25° C (excursions permitted between 15°C and 30°C). A one to three week supply of the cream will be dispensed to the subject during study participation, with the exception that a 2 - 3 week supply will be provided at the time of CT Simulation (determined by the anticipated radiation start date). The same method will be used for the dispensing of the Aquaphor except that refrigeration will not be done in the pharmacy.

Patients will be instructed to apply the cream/Aquaphor along the area exposed to radiation from the day of simulation to two weeks after completion, correlating with the acute phase of radiation dermatitis. If the time from CT Simulation to start of radiation is greater than 2 weeks then the patient may be instructed to start the cream/Aquaphor 2 weeks prior to the anticipated start of radiation rather than at the time of CT Simulation. In the event of a delay from the time of CT simulation to the start of XRT, if the patient has no more than 3 days of interruption of the cream, this will not be considered a violation of the protocol. An interruption longer than 3 days will be considered a minor deviation. Patients who develop moist desquamation in the radiation treatment area may be prescribed a topical antibiotic or other standard of care treatment if indicated. Subjects will be instructed to not use other lotions, creams or any other products in the radiation treatment area without the study doctor's approval.

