8 STATISTICAL CONSIDERATIONS

8.1. Study Design/Endpoints

This portion of the study is designed to evaluate toxicity profile and preliminary efficacy of prophylactic Dermaprazole cream for radiation dermatitis in head and neck cancer patients receiving chemoradiation.

The first primary outcome is rates of clinically significant radiation dermatitis as defined as NCI CTCAE version 5 grade 2 or higher. Although not expected, if half our expected enrollment in the Dermaprazole group, 50% or more of patients experience moderate intervention-related toxicity, this treatment regimen will not be considered safe. The trial will be monitored for SAEs and stopped early for safety if two treatment-related grade 3 SAEs are reported or if one treatment-related grade 4-5 SAE is reported at any point of the trial for the Dermaprazole group.

Another primary endpoint will be feasibility, which is defined as the consideration of whether the protocol implementation will be successful in terms of accrual within the expected timeframe, as well as whether patients would comply with the study protocol and necessary data collection is logistically feasible in the clinical setting. To evaluate feasibility, we will measure:

Page 14 of 23

- Accrual rate and summary of causes for non-enrollment
- Percentage of patients compliant with therapy, defined as receiving at least 60Gy to the head and neck while using prophylactic Dermaprazole as directed
- Compliance rate and rate of completion of SkinDex16 forms

All endpoints will be evaluated when the last patient completes their 3 Month follow-up visit, although patients will continue with additional regular follow-up visits as described in the protocol schedule. Since by that point a patient would have completed all treatments, the data would provide accurate estimate of compliance and acute toxicity.

For the study to be considered feasible, all of the following must be true:

- No more than 5 patients fail to complete the treatment regimen due to study drug toxicity
- No more than 15 patients fail to comply to prophylactic Dermaprazole cream application of at least 80%
- Enrollment takes no longer than 24 months, and
- Proportions of analyzable questionnaires at baseline, while on-treatment, and offtreatment during follow-up, and within questionnaires completion rates are no worse than 80%, 80%, and 60% respectively.

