8.2 Sample Size/Accrual Rate

Participants will continue to be enrolled and monitored for toxicity per the above criteria until 30 patients in arm 1 and 15 patients in arm 2 have completed the course of head and neck radiation as evaluable patients. Patients will be randomized by computer in a 2:1 fashion. Per our current database, the clinic is treating approximately 60 eligible patients per year. As such, accrual should take no longer than 12 months but will be allowed to extend to up to 24 months without closing the study.

Initial sample size for this pilot study was estimated as if this study was conducted as a phase II study. Sample size calculation was determined using significance/alpha (α) of 0.05, to at least detect a difference in incidence of 45% and power (β) of 80%. In general, rates of clinically bothersome grade II dermatitis in the literature appear to be approximately 65%. Based on our preclinical study with animal and human skin models, we expect 20% of the Dermaprazole arm to have CTCAE grade II or higher RD. Given these values, we calculated our final sample size to be approximately 39 and we aim to enroll 45 subjects.

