10.4 Management of Adverse Events and impact on treatment

- Expected mild/moderate toxicity (Grade 1-2) will be managed conservatively by the treating physician.
- Unexpected or severe adverse events will be managed on a case by case basis at the discretion of the treating physician in coordination with the study team. Emergent dermatology consult and face-to-face evaluation within 48 hours will be sought for each suspected intervention-related adverse effect. Every effort will be made to continue radiation treatments for the prescribed duration, as would be the standard of care. If the risks of continuation of any portion of the patients' treatment is felt to immediately outweigh the benefits or be detrimental to the patient, it may be temporarily withheld at the discretion of the treatment team.
- Adverse events directly related to Dermaprazole may prompt withdrawal from the study. Radiation will continue as scheduled unless Grade 4 toxicity occurs, in which case delay to allow for healing is permitted.

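### Section 8.4 restricts the analysis to patients who reach 60 Gy and day 30, so dermatitis already recorded can drop out of the primary comparison

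*Combined protocol and SAP*

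**What the plan says.** Section 8.4 is the only rule on who is analysed: enrolled patients "who complete at least 60Gy of radiation and follow up at 30 days post treatment will be included in the analysis". Section 8.3 refers to all enrolled subjects, but only for descriptive demographic and clinical data.

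Other sections bear on who meets that rule:

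- **Outcome timing (2.1.1).** On grade 2 or higher dermatitis: "This measure will be reported weekly during treatment by both the treating radiation oncologist" and by a dermatologist reading photographs blind.
- **Accrual (8.2).** Enrolment runs "until 30 patients in arm 1 and 15 patients in arm 2 have completed the course of head and neck radiation as evaluable patients", with 45 as the enrolment aim.
- **Feasibility (8.1).** Compliance with therapy is "defined as receiving at least 60Gy to the head and neck while using prophylactic Dermaprazole as directed".
- **Radiation changes (5.4).** Variations, including dose adjustments, "that follow standard clinical practice are allowed and are not considered deviations".
- **Dermatitis and early stopping (3.1).** "Severe dermatitis can result in discontinuation of the radiotherapy before completion of the prescribed dose"
- **Product reactions (10.4).** "Adverse events directly related to Dermaprazole may prompt withdrawal from the study" The same section limits interruption of radiation: "Radiation will continue as scheduled unless Grade 4 toxicity occurs, in which case delay to allow for healing is permitted"

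**The concern.** Randomisation makes the arms comparable at baseline. A set chosen by what happens afterwards keeps that comparability only if the selection is unrelated to outcome and arm. Here the protocol names a link to each: dermatitis can end radiation early, and a Dermaprazole reaction can end participation, a route that by its wording exists in one arm.

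This is not a missing-data problem. In the case at issue the grade has been recorded and the rule removes it. Because 8.2 keeps enrolling until 30 and 15 have completed radiation, non-completers are in effect replaced, and the final denominators would not show that anyone was lost.

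At stake is the primary between-arm comparison. If 8.4 is also read as governing the safety rates in 8.3, the safety verdict is at stake too, for a cream that 10.3 describes as not yet tested in humans.

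**Working it through.** **Inputs.** Rates of 65% on Aquaphor and 20% on Dermaprazole, alpha 0.05 and 80% power (8.2); 2:1 allocation (5.2); chi-square, two-sided tests (8.3); 30 and 15 analysed (8.2). The share x of patients with the event who are lost is an assumption: 5, 10, 20 or 30%.

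**The plan's own figure.** With k = 2 and pooled rate (0.65 + 2 × 0.20)/3 = 0.35,

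n(control) = [1.960 × √(0.35 × 0.65 × 1.5) + 0.842 × √(0.65 × 0.35 + 0.20 × 0.80/2)]² / 0.45² = 12.8, rounded up to 13.

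So 13 + 26 = 39, as stated. The sample size is not in question.

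**Effect of selection, with replacement.** If a share x of patients with events is lost and replaced, the event rate among those analysed is p(1 − x) / [p(1 − x) + 1 − p]. For p = 0.65 and x = 0.20 this is 0.52/0.87 = 0.598. Rejection probabilities come from exact binomial enumeration at 30:15 with the uncorrected chi-square test.

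| x | 0 | 5% | 10% | 20% | 30% |
|---|---|---|---|---|---|
| Analysed rate when p = 0.65 | 0.650 | 0.638 | 0.626 | 0.598 | 0.565 |
| Analysed rate when p = 0.20 | 0.200 | 0.192 | 0.184 | 0.167 | 0.149 |
| Both true rates 65%, loss on Dermaprazole only: two-sided false positives | 0.0515 | 0.0510 | 0.0520 | 0.0596 | 0.0778 |
| Of these, favouring Dermaprazole | 0.0243 | 0.0286 | 0.0339 | 0.0486 | 0.0718 |
| 20% v 65%, loss on control only: power | 0.863 | 0.846 | 0.825 | 0.776 | 0.710 |
| 20% v 65%, equal loss: power | 0.863 | 0.862 | 0.860 | 0.853 | 0.842 |

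**Without replacement.** Here 30:15 are randomised and each event is dropped with probability x. For x = 5/10/20/30%:

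- false positives, loss on Dermaprazole only: 0.0516/0.0535/0.0629/0.0822;
- power, loss on control only: 0.836/0.807/0.736/0.646;
- power, equal loss: 0.852/0.843/0.817/0.783.

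The replacement figures fit patients who stop radiation early, since 8.2 counts completers. The figures without replacement are closer to patients who miss only day 30, because 8.2 does not clearly replace them.

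**Single tables.** A result of 6/30 v 10/15 (p = 0.002) survives restoring five excluded Dermaprazole events (11/35, p = 0.021), and even eight (14/38, p = 0.049). A result of 9/30 v 10/15 (p = 0.019) does not survive restoring three (12/33, p = 0.051).

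**Safety, only if 8.4 governs it.** Section 8.3 requires a grade 2 or higher toxicity rate below 10%, so at most 2 of 30. Thus 2/30 = 6.7% passes, 3/31 = 9.7% still passes with one event restored, and 4/32 = 12.5% fails with two restored. One excluded grade 3 event reverses the requirement that there be none. At an assumed true rate of 15%, the chance of meeting the 10% limit rises from 0.151 to 0.175/0.201/0.265/0.345 as x goes from 0 to 5/10/20/30%. At an assumed 5%, it rises from 81% to 83/85/88/91%.

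**Feasibility.** Everyone in the 8.4 set has had at least 60 Gy, so that part of the 8.1 compliance measure would be met by definition. The measure needs a wider denominator, and none is stated.

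**The case against.** The strongest reply is that losses may be few and the effect then negligible. Section 10.4 continues radiation unless there is Grade 4 toxicity, and then permits delay, not truncation. Stopping the cream does not stop radiation, so such a patient can still reach 60 Gy and day 30. The statement about early stopping in 3.1 is disease background, 4.1 requires at least 60 Gy to be planned, and the day-30 window is ±14 days (5.6). Nothing links a missed day 30 to dermatitis. A material effect needs about 20 to 30% of events lost in one arm: with both rates at 65%, 3.9 to 5.9 of an expected 0.65 × 30 = 19.5 Dermaprazole events. All of this stands as a limit on size, but it does not put an excluded patient back into the comparison.

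The safety argument is conditional. Section 8.4 does not claim the 8.3 rates, and 8.3 speaks of each recorded event. Section 5.7 follows ongoing drug-related events, 10.5 records all SAEs, and neither the SAE stopping rule nor the toxicity-failure count in 8.1 is tied to 8.4. That stands too; the remaining gap is that no denominator is given. The same answer applies to feasibility: the 8.1 failure counts imply that non-completers are included, but the plan does not say so.

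Finally, an all-randomised set includes patients with little radiation exposure, who may count as non-events. A set of all who started radiation and product would also deal with most of the problem. But starting is itself after randomisation, and the plan describes only the dermatologist's review as blinded. The exposure point is a fair limit, and is why exclusions should be shown by arm and reason.

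**Conclusion.** The concern holds. As written, the only analysis set conditions on two post-randomisation events and can discard primary outcomes already on record. That is certain from the text. The size of any bias is not, because the documents give no loss rate. At 5 to 10% loss of events in one arm, the two-sided error rate is essentially unchanged and power falls by at most about 4 points with replacement (6 without). At 30%, false positives reach about 8%, and loss on control only lowers power to 71% (65% without replacement). Losses on Dermaprazole favour it; losses on control can hide a real effect. The safety figures apply only if 8.4 is read as covering 8.3. This should be fixed before analysis.

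**What to change.** Replace 8.4 with:

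> The primary endpoint is analysed in all randomised patients by assigned arm, using the worst dermatitis grade at any post-baseline assessment made for that endpoint, whether or not 60 Gy or day 30 was reached. The 8.3 safety rates include all patients who applied any study product. Feasibility and compliance measures use all randomised patients (Dermaprazole compliance: all randomised to Dermaprazole). The set reaching at least 60 Gy and day 30 is supportive. Patients outside the supportive set, and patients never graded after baseline, are reported by arm and reason. Sensitivity analyses count the never-graded as events and as non-events.

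How the never-graded count in the main analysis is the sponsor's choice, fixed in advance. This wording settles the population only; the assessment window and which rater's grade counts must also be named. If 8.2 keeps enrolling to 30 and 15 completers, non-completers must stay in the primary and safety analyses.

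The cost is protocol wording, an exclusions table and a little more analysis; the calculated 39 stands. At 20% v 65% with 30:15, if 2/5/10% were never graded, power in the sensitivity analyses is 84/81/75% counting them as events and 85/83/80% as non-events, against 86% with none. Weekly grading from week 1 should keep that number small. These figures do not allow for shortened exposure in patients who stop early.

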9 DATA MANAGEMENT

Patient information will be acquired from patient medical records within the clinical site Electronic Medical Record (EMR) system.

Page 16 of 23

Patient characteristics including age, race/ethnicity, initial biopsy result, cancer stage, BMI and known comorbidities will be collected.

Patient data for analysis will be captured using REDCap. Paper forms including the skindex16 questionnaires will be kept in a locked cabinet in the Radiation Oncology offices and input into REDCap. Photos of patients' skin reaction will also be kept on this limited-access network drive. Patient information will be de-identified for final statistical analysis by removal of patient names and MRNs. Each patient will be assigned a study code at time of study registration.

Information gathered from the planning system will include the V20 to V80 in 5 Gy increments reaching skin shell contours of "skin minus 3 millimeters" and "skin minus 5 millimeters" as well as the total dose. This will be collected for both simulation scans.

10 DATA AND SAFETY MONITORING

10.1 Data and Safety Monitoring Oversight:

A Data and Safety Monitoring Plan (DSMP) is required for all protocols conducted at MAYS CANCER CENTER. All protocols conducted at MAYS CANCER CENTER are covered under the auspices of the MAYS CANCER CENTER Institutional Data Safety Monitoring Plan. The MAYS CANCER CENTER Institutional DSMP global policies provide individual trials with:

- institutional policies and procedures for institutional data safety and monitoring,
- an institutional guide to follow,
- monitoring of protocol accrual by the MAYS CANCER CENTER Protocol Review Committee,
- review of study forms and orders by the Forms Committee,
- tools for monitoring safety events,
- monitoring of UPIRSO's by the Director of Quality Assurance and DSMC,
- determining level of risk (Priority of Audit Level Score PALS),
- oversight by the Data Safety Monitoring Committee (DSMC), and
- verification of protocol adherence via annual audit for all Investigator Initiated Studies by the MAYS CANCER CENTER Quality Assurance Division.

10.2 Monitoring Safety:

The PI or treating investigator will perform primary assessment of adverse events, adverse event trends and treatment effects on this study. The PI will conduct independent quarterly reviews and report findings to the MAYS CANCER CENTER Data Safety Monitoring Board (DSMB) and the UT HEALTH IRB. Baseline events and adverse events will be captured using the MAYS CANCER CENTER Master Adverse Events Document for each patient using CTCAE v5.0 for the grading and attribution of adverse events. Usage of the MAYS CANCER CENTER Master Adverse Events Document centrally documents:

- the event and grades the seriousness of it,
- if the event was a change from baseline,

Page 17 of 23

- determines the relationship between the event and study intervention,
- if the event was part of the normal disease process, and
- what actions were taken as a result of the event.

	Grade 1	Grade 2	Grade 3	Grade 4	Grade 5
Symptoms or Signs	or Asymptomatic or mild Moderate limiting age appropriate instrumental ADLs		Severe, not immediately life threatening. Disabling, limiting self-care ADLs	Life threatening	Death related to AE
Intervention	Observation	Local or non- invasive intervention	Hospitalization	Urgent/ emergent intervention	-

10.3 Safety Definitions: For this study, the following safety definitions will be applicable:

Adverse Event Definition:

An adverse event (AE) is defined as any untoward or unfavorable medical occurrence in a human subject, including any abnormal sign (for example, abnormal physical exam or laboratory finding), symptom, or disease, temporally associated with the subject's participation in the research, whether or not considered related to the subject's participation in the research.

The adverse event (AE) collection/reporting period will begin with the first day of treatment with radiation or chemotherapy. AEs after study registration but prior to the first day of study treatment will be captured as ongoing concurrent secondary diagnoses and symptoms present at the start of study.

Serious Adverse Event Definition: is any adverse event that:

- 1. results in death;
- 2. is life-threatening (places the subject at immediate risk of death from the event as it occurred);
- 3. results in inpatient hospitalization or prolongation of existing hospitalization;
- 4. results in a persistent or significant disability/incapacity;
- 5. results in a congenital anomaly/birth defect; or
- 6. based upon appropriate medical judgment, may jeopardize the subject's health and may require medical or surgical intervention to prevent one of the other outcomes listed in this definition.

Page 18 of 23

Unanticipated Problems Involving Risks to Subjects or Others Definition:

Unanticipated problem involving risk to subjects or others includes any incident, experience or outcome that meets all of the following criteria:

A. unexpected (in terms of nature, severity, or frequency) given

- (a) the research procedures that are described in the protocol-related documents, such as the IRB-approved research protocol and informed consent document; and
- (b) the characteristics of the subject population being studied (note: the unfounded classification of a serious adverse event as "anticipated" constitutes serious non-compliance);

B. definitely related or probably related to participation in the research; and C. suggests that the research places subjects or others at a greater risk of harm (including physical, psychological, economic, or social harm) than was previously known or recognized.

Expected adverse events are those that have been previously identified as resulting from administration of topical or radiation therapy.

For purposes of this study, an adverse event is considered expected when the events are those related to systems within the radiation treatment field and include: infection, allergy, or short & long-term (greater than 6 month) skin changes.

Radiation: The common side effects of radiation to the head and neck most commonly includes radiation dermatitis (i.e., erythema, blistering, pigmentation changes) and fibrosis/firmness of head and neck in the long-term. Commonly, patients develop dry mouth, changes in taste, pain when swallowing, and weight loss. Long term, some patients can continue to have changes in taste and lymphedema.

Dermaprazole: The interventional cream is not yet tested in humans and reactions *in* vivo (especially in patients experiencing radiation dermatitis) are not yet known. Possible side effects include allergy or infection. Given the success in pre-clinical studies, it is unlikely that the interventional cream would lead to worsened rates of radiation dermatitis and skin integrity, though this is a possibility.

Acute and late designations will be defined by the timing of occurrence from treatment.

- Acute toxicity will be defined as events occurring during or within 90 days of treatment completion.
- Late toxicity will be defined as events occurring or persisting ≥90 days from treatment completion.

Attribution: An attribution scale which will be utilized to attribute relatedness of the adverse event to the radiation treatment or to the Dermaprazole/Aquaphor as determined by the treating investigator or Principal Investigator. Assignment of attribution is the responsibility of the treating investigator or Principal Investigator.

Page 19 of 23

- Definite The AE is clearly related to the study treatment.
- Probable The AE is likely related to the study treatment.
- Possible The AE may be related to the study treatment.
- Unlikely The AE is doubtfully related to the study treatment.
- Unrelated The AE is clearly NOT related to the study treatment.

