10.5 Reporting Requirements

The adverse event (AE) collection/reporting period for events related to Aquaphor or Dermaprazole will begin with the first day of application of the product. The adverse event (AE) collection/reporting period for all other events will begin with the first day of treatment with radiation or chemotherapy. AEs not related to Aquaphor or Dermaprazole that occur after study registration but prior to the first day of study treatment will be captured as ongoing concurrent secondary diagnoses and baseline symptoms present at the start of study.

The following adverse events, regardless of perceived relationship to study treatment, will be reported and recorded:

- Scarring, fibrosis, epilation, or pigmentation changes that extend beyond 6 months
- Anaphylaxis, hypotension, urticarial, or other reactions felt to be allergic
- All SAEs
- Adverse events (AEs) and serious adverse events (SAEs) that are ongoing at the
 end of the treatment and related to radiation treatment or investigational
 product application (but not chemotherapy) or lab abnormalities specified on the
 Study Calendar will be followed until resolution or the end of study follow-up.

Page 20 of 23

For this study, all Master Adverse Events Documents collected on patients for this protocol will be reviewed by the Principal Investigator on a quarterly basis to determine if a serious safety problem has emerged that results in a change or early termination of a protocol such as:

- suspending enrollment due to safety or efficacy, or
- termination of the study due to a significant change in risks or benefits.

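### Sections 10.3 and 10.5 disagree on when product-related adverse events start to count, and the calendar has no adverse event check before radiotherapy or in the last two weeks of application

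*Combined protocol and SAP*

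**What the plan says.** Section 10.3 sets one start date for all adverse events: "The adverse event (AE) collection/reporting period will begin with the first day of treatment with radiation or chemotherapy". It makes no exception for the study product. On earlier events it says: "AEs after study registration but prior to the first day of study treatment will be captured as ongoing concurrent secondary diagnoses and symptoms". The term study treatment is not defined there.

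Section 10.5 splits the rule. The period for "events related to Aquaphor or Dermaprazole will begin with the first day of application of the product"; all other events start with radiation or chemotherapy. Its baseline rule is limited to "AEs not related to Aquaphor or Dermaprazole that occur after study registration but prior to the first day of study treatment".

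Under 5.4, patients apply the product from simulation, or from two weeks before radiotherapy when the gap is longer, until two weeks after radiotherapy ends. The calendar in 6.1 marks the product at Baseline and Weeks 1 to 9, and marks Adverse Events/Toxicity at Weeks 1 to 7 only. The next adverse event check is the Month 1 visit, 30 days after radiotherapy with a window of 14 days either side.

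Recording does not stop outside those weeks. Under 10.2, "Baseline events and adverse events will be captured using the MAYS CANCER CENTER Master Adverse Events Document for each patient", and 10.5 adds that "all Master Adverse Events Documents collected on patients for this protocol will be reviewed by the Principal Investigator on a quarterly basis".

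**The concern.** Section 10.3 states of the product: "The interventional cream is not yet tested in humans". Section 8.3 gives its safety and tolerability profile as the primary intention of the study. The lead-in is the only time patients use the product before radiation begins. A skin reaction then cannot be radiation dermatitis, which makes it the easiest reaction to attribute to the product. Staff who follow 10.3 as written could file it as a symptom present at the start of study, while staff who follow 10.5 would record an adverse event.

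The analysis section does not resolve this. The acute toxicity window in 8.3 covers the radiotherapy course and the 90 days after it, and does not mention events before it.

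The calendar matters for a related reason. During the lead-in and the last two weeks of application, no scheduled visit item asks about adverse events. Reactions in those periods come to light through patient self-report (5.4), unscheduled routes (5.7 and 10.4), or recall at Week 1 or Month 1.

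**Working it through.** **1. The two start rules side by side**

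| Event | Section 10.3 | Section 10.5 |
|---|---|---|
| Product-related, after first application, before radiation or chemotherapy | Before the collection period opens | Adverse event |
| Not product-related, same period | Before the collection period opens | Baseline symptom |
| Any event from radiation or chemotherapy onward | Adverse event | Adverse event |

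The sections differ only in the first row.

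Could 10.3 be read to agree with 10.5? The attribution scale in 10.3 is used to "attribute relatedness of the adverse event to the radiation treatment or to the Dermaprazole/Aquaphor", so study treatment might be taken to include the product. That would bring the second sentence of 10.3 into line. The first sentence still names only radiation or chemotherapy, so the conflict remains. Calendar footnote (k) points to 10.5, but it is attached only to the post-treatment adverse event row and not to the lead-in.

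**2. Calendar count (6.1, no assumption needed)**

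- Product row: Baseline and Weeks 1 to 9 = 10 columns.
- Adverse Events/Toxicity row: Weeks 1 to 7 = 7 columns.
- Product but no adverse event check: 10 − 7 = 3 columns (Baseline, Week 8, Week 9).
- The radiation oncologist's CTCAE dermatitis row is blank in the same three columns.
- The compliance row is marked in two of the three (Baseline and Week 9).

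**3. Month 1 against the end of application**

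Application is planned to end on day 14 after radiotherapy.

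- Nominal: 30 − 14 = 16 days after the last application.
- Window: day 30 − 14 = 16 to day 30 + 14 = 44, which is 16 − 14 = 2 to 44 − 14 = 30 days after the last application.

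Month 1 therefore always falls after planned application has ended.

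**4. The same gap in days (assumptions stated)**

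Assume 2 Gy per fraction, 5 fractions a week. Then 60 to 70 Gy is 30 to 35 fractions, or 6 to 7 weeks = 42 to 49 days. Application after radiotherapy is 14 days.

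Share outside the radiotherapy weeks = (lead-in + 14) / (lead-in + radiotherapy days + 14).

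| Lead-in | 42 days of radiotherapy | 49 days of radiotherapy |
|---|---|---|
| 14 days | 28/70 = 40% | 28/77 = 36% |
| 0 days | 14/56 = 25% | 14/63 = 22% |

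These shares describe the schedule. They do not estimate missed events.

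**5. Why one event's classification can matter**

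The 8.3 safety criterion requires a grade 2 or higher toxicity rate below 10% and no event of grade 3 or higher. If all 30 Dermaprazole patients are analysed, 2/30 = 6.7% meets the rate limit and 3/30 = 10% does not. This shows the criterion's sensitivity to single patients and predicts nothing about the result.

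**The case against.** The strongest reply is that 10.3 contains a leftover sentence and 10.5 is plainly the operative rule. It is the more specific text, it deals with reporting, and a lead-in reaction that clearly belongs to the product is just what it covers. Several safeguards also limit the harm:

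- 10.5 requires allergic reactions and all serious adverse events to be recorded whatever their perceived cause.
- The stopping rule in 8.1 covers treatment-related serious events of grade 3 to 5 at any point in the trial.
- The safety criterion in 8.3 is not worded as limited to acute events, so the acute window does not by itself exclude a pre-radiotherapy event.
- Weekly checks may be 3 days late, so the last one can fall just after radiotherapy. Week 9 includes a research blood draw, so the patient is in contact then.
- 10.4 seeks a face-to-face dermatology evaluation within 48 hours of a suspected product effect.

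On the calendar, an adverse event check at the Baseline visit itself would come before or at first exposure, so the practical gap is the missing adverse event item at the pre-radiotherapy contact and at Week 9. No text promises checks in those periods, so the schedule does not contradict itself.

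These points are correct and narrow the consequence. They do not remove the conflict, because no text ranks the two sections. They also leave uncovered non-serious, non-allergic local reactions such as burning or tenderness, which the study summary lists among the effects to be assessed. A 3-day allowance does not cover 14 days, and the 10.4 evaluation begins only once an effect is suspected.

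**Conclusion.** The point holds, with high confidence. Sections 10.3 and 10.5 give different answers for product-related events between first application and the start of radiation or chemotherapy, and they must be reconciled. Separately, 3 of the 10 calendar columns with product use have no scheduled adverse event check, and the next check comes nominally 16 days (2 to 30 within its window) after application ends. Both statements come straight from the text. Only the day-based shares need assumptions: 36 to 40% with a 14-day lead-in and 22 to 25% with none, at 2 Gy per fraction.

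The consequence is limited to classification and scheduled ascertainment of safety events. Lead-in events can still be recorded, graded and attributed. No effect on the primary dermatitis measure and no change in the safety verdict is claimed. The change should be made because the product is new to humans and the remedy is cheap.

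**What to change.** 1. In 10.3, replace the sentence on the start of collection and the sentence on earlier events with the 10.5 wording, and define study treatment to include Dermaprazole and Aquaphor. Add one sentence to 8.3 stating that product-related events from first application count toward the safety criterion.
2. Add the Adverse Events/Toxicity item to the pre-radiotherapy compliance contact and to Week 9. State when the pre-radiotherapy contact takes place, since footnote (f) gives neither number nor timing; the end of the lead-in would cover the whole of it. Week 9 is nominally the last day of application, with a window of 5 days either side.

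The first change is a wording amendment. The second adds a few questions at two contacts already in the calendar. Neither alters the product's application or the visit schedule, beyond fixing the time of one contact.

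Two limits remain. Classification still depends on the investigator's attribution. The analysis set in 8.4 is also unchanged, so a patient who leaves before 60 Gy or before the 30-day follow-up is outside the analysis under either wording.
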